8.6 Lifestyle Restrictions

Subjects will be advised to adhere to the restrictions detailed in the following subsections.

8.6.1 Alcohol Restrictions

Subjects are prohibited from excessive consumption of food or drink containing alcohol. Over the course of the study, subjects should not exceed 8 grams (equates to approximately 1 drink [1 glass of wine; one 12-ounce beer; 1 mixed drink/cocktail]) of alcohol per day.

8.6.2 Contraception

Subjects must agree to use 2 forms of nonhormonal dual contraception consistently throughout the study and until 3 months after the last dose of study drug. After Week 16 (Visit 9), if preferable, the subject may begin the use of hormonal contraception in place of nonhormonal dual contraception. Subjects must have negative urine pregnancy tests during the Screening period and a negative urine pregnancy test prior to the first dose of study medication on Day 1. Acceptable methods of dual contraception include the following combinations:

[figure not shown]
- Condoms used with spermicide (cream, spray, foam, gel, suppository, or polymer film);
- Diaphragm used with spermicide (condom may or may not be used);
- Cervical cap used with spermicide (condom may or may not be used);
- Vaginal sponge impregnated with spermicide used with a condom.

[figure not shown]
Subject is not required to use dual contraception methods if:

[figure not shown]
- Sexual partner(s) has undergone male sterilization (eg, vasectomy, at least 6 months prior to Screening or with the appropriate postvasectomy documentation of the absence of sperm in the ejaculate, bilateral orchiectomy);
- Subject has had a bilateral tubal occlusion (including ligation and blockage methods such as Essure[®]), at least 3 months prior to Screening;
- Subject is not sexually active with men; periodic sexual relationship(s) with men requires

the use of nonhormonal contraception as indicated above;

• Hormonal contraception is started 3 months after the last dose of study drug.

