7 STUDY DESIGN

7.1 Overall Study Design

7.1.1 Study Methodology

This is a Phase 2, randomized, double-blind, placebo-controlled study, stratified by moderate or severe pain to evaluate safety and efficacy of MT-2990 in women with endometriosis-associated moderate to severe pain. Approximately 76 subjects will be randomized into the study, with approximately 38 subjects in each treatment arm. The approximate duration of the study per subject is 52 weeks, inclusive of the Screening period, Double-blind Treatment period, and the Extended Follow-up period.

Following the Screening period, eligible subjects who have met all the eligibility criteria and have moderate or severe nonmenstrual pelvic pain, and dysmenorrhea will be randomized into the study. Approximately 38 subjects per arm will be enrolled. Subjects will be randomly allocated to 1 of 2 treatment groups (placebo or MT-2990 in a ratio of 1:1.

All efficacy and safety measures will be collected during the 16-week Double-blind Treatment period.

End-of-treatment (EOT) will occur at Week 12 (Visit 7) and primary and secondary efficacy endpoints will be assessed at the Week 16 (Visit 9) visit. Subjects who discontinue from the study will complete the procedures for Visit 9 within 10 days of discontinuation (or as soon as possible after the site becomes aware of the discontinuation).

During the Extended Follow-up period, visits will be conducted via a telephone call at Week 27 (Visit 10) and at Week 38 (Visit 11).

The Sponsor will be unblinded after Week 16 (Visit 9), while the Sites and subjects will remain blinded until the end of the Extended Follow-up period at Week 38 (Visit 11). During the study, database will be locked twice: at Week 16 (Visit 9) to assess safety and efficacy, and at Week 38 (Visit 11) to assess other outcomes during the Extended Follow-up period.

There will be 3 interim assessments for safety. The first interim assessment for safety will be performed when 20 subjects are randomized and have completed the Week 2 visit. The second interim assessment for safety will be performed when 50% of the subjects are randomized and have completed the Week 4 visit. The third interim assessment for safety will be performed when 50% of the subjects are randomized and have completed the Week 16 visit.

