8.3 Subject Inclusion Criteria

1. Subject must sign the written informed consent form (ICF) to participate in this study.

Inclusion Criteria for Entry into the Washout Period (if applicable [in addition to Inclusion Criteria 5 through 9]):

3. Subject agree to approximately 90-day washout interval of hormonal therapies, if applicable.

[figure not shown]
Inclusion Criteria for Entry into the Screening Period

- 4. Subject undergoing the Washout period (if applicable), must have a menstrual cycle with an interval of 21 to 38 days prior to entering the Screening period.
- 5. Subject must have a body mass index < 45 kg/m² (inclusive) at Screening and Day 1.
- 6. Subject who has documented surgical/laparoscopy diagnosis of endometriosis within 10 years of the Screening period.
- 8. Subject agrees to use 2 forms of nonhormonal contraception throughout the study (refer to Section 8.6.2).

9. In the Investigator's opinion, subject is able to understand the nature of the study and any risk involved in participation and is willing to cooperate and comply with the protocol restrictions and requirements including TVU.

Inclusion Criteria for entry into the Double-blind Treatment Period

11. Subject must have had 2 menstrual cycles with an interval of 21 to 38 days prior to treatment Day1.

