10.4.2 Prohibited Medication

Subjects must not participate in any other clinical study involving administration of an IMP for the duration of the current study.

Subjects must not take any prescribed or nonprescribed systemic or topical medication (including herbal remedies) unless, in the opinion of the Investigator and Sponsor, the medication will not interfere with the study procedures or compromise safety.

Subjects must not take hormonal contraceptives.

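### Protocol Section 8.6.2 gives two different start times for hormonal contraception, and the visible ban in Section 10.4.2 makes no exception for either

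*Protocol*

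**What the plan says.** Section 8.6.2 of the protocol makes three statements about timing.

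- The general requirement is "2 forms of nonhormonal dual contraception consistently throughout the study and until 3 months after the last dose of study drug".
- The next sentence is a dated permission: "After Week 16 (Visit 9), if preferable, the subject may begin the use of hormonal contraception in place of nonhormonal dual contraception".
- The list of situations in which dual methods are not required ends with this one: "Hormonal contraception is started 3 months after the last dose of study drug".

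Two other places bear on the same question.

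- Section 10.4.2 states "Subjects must not take hormonal contraceptives". No end date or exception is visible.
- Inclusion criterion 8 in Section 8.3, repeated in the Synopsis, reads "Subject agrees to use 2 forms of nonhormonal contraception throughout the study (refer to Section 8.6.2", so it sends the reader to 8.6.2 for the detail.

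On timing, Section 7.1.1 says "End-of-treatment (EOT) will occur at Week 12 (Visit 7) and primary and secondary efficacy endpoints will be assessed at the Week 16 (Visit 9) visit". Follow-up then continues by telephone to Week 38 (Section 9.1.4).

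**The concern.** A site asked when a woman may start a hormonal method finds two answers in one section and an unqualified prohibition in another. Contraception after exposure is a subject-protection matter: Section 12.9 requires pregnancies in exposed women to be reported on the same timelines as serious adverse events. After Visit 9 the only scheduled contacts are two telephone calls, so advice that differs between sites would be hard to notice and correct.

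There is also a bookkeeping consequence. SAP Section 8.1.6 lists prohibited medication. A woman who starts a hormonal product on the strength of the Week 16 sentence is compliant under that sentence but is taking a prohibited medication under Section 10.4.2.

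**Working it through.** The documents state no calendar week for the 3-month point, so there is no figure of theirs to reproduce. It has to be derived.

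**Inputs**
- Last planned dose: Week 12. Section 7.1.1 puts end of treatment there. Section 10.18.2 places the post-infusion vital signs at Visits 2, 5, 6 and 7. SAP Section 7.1.1.2 gives four doses, one every four weeks, hence Day 1 and Weeks 4, 8 and 12.
- Permission: after Week 16 (Visit 9).
- Three months: taken as 84 to 92 days, because the protocol does not define it in days.

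**Subjects who complete dosing**

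Formula: week of 3-month point = 12 + days/7; gap = that week − 16.

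| Three months taken as | 3-month point | Gap after Week 16 |
|---|---|---|
| 84 days | 12 + 12.0 = Week 24.0 | 8.0 weeks |
| 91 days | 12 + 13.0 = Week 25.0 | 9.0 weeks |
| 92 days | 12 + 13.1 = Week 25.1 | 9.1 weeks |

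**Subjects who stop dosing early** (three months taken as 365.25/4/7 = 13.04 weeks)

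| Last dose | 3-month point | Relative to Week 16 |
|---|---|---|
| Day 1 only | about Week 13 | about 3 weeks before |
| Week 4 | about Week 17 | about 1 week after |
| Week 8 | about Week 21 | about 5 weeks after |

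So the order of the two dates can reverse. A further ambiguity arises because discontinuing subjects complete the Visit 9 procedures within 10 days of discontinuation (Section 7.1.1). The permission names both a week and a visit and does not say which governs. If the visit governs, the permission could open shortly after the last dose. If the week governs, a woman dosed only on Day 1 passes the 3-month point before the permission starts.

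**The statements side by side, for a woman last dosed at Week 12 who starts a hormonal method at Week 20**
- The Week 16 sentence allows it.
- The exemption bullet does not cover it, because 20 − 12 = 8 weeks, which is less than 3 months.
- The general requirement does not allow it unless the Week 16 sentence is read as an exception.
- Section 10.4.2, as visible, does not allow it at any time.

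**The case against.** The best defence is that the first two sentences of 8.6.2 are a rule followed by its exception: nonhormonal methods in general, with a dated release after Week 16. The exemption bullet then gives one sufficient condition and does not, by its wording, forbid an earlier start. That reading is fair for the first two sentences. It does not dispose of the point. If Week 16 already releases a woman who completed dosing, a bullet that releases her at Week 24 to 25 has no work to do, and its presence suggests a different rule. The reading also leaves Section 10.4.2 without any matching exception.

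Other parts of the defence stand in full and limit the point.

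- Inclusion criterion 8 refers to 8.6.2 and takes its meaning from there. It is not a separate conflict.
- A reader might infer a conflict lasting the whole of follow-up, 38 − 16 = 22 weeks. That needs criterion 8 as an independent rule, or the general requirement read without the Week 16 exception, or Section 10.4.2 read as truly undated. The first fails, the second is not the only reading, and text near 10.4.2 may be blacked out.
- A reader might infer that hormonal use biases the Extended Follow-up results. The documents do not support that. The e-Diary covers only Screening and the Double-blind Treatment period (Section 13.5), visible efficacy endpoints with a stated time frame end by Week 16, and the exploratory endpoints are not visible, so no affected follow-up outcome can be named. Any such mixing would come from the Week 16 permission itself and would remain if the text were unified on that permission.
- A reader might infer that deviations cannot be classified at all. Important deviations are settled at a data review before database lock (SAP Section 5), and a start after Week 16 cannot alter Week 16 data.
- Concomitant medication is recorded in the eCRF to the end-of-study visit (Section 10.4), summarised by treatment group (Section 14.3.4.7) and listed with prohibited medication (SAP Section 8.1.6).

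**Conclusion.** The contradiction is real and narrow. Within Section 8.6.2, the Week 16 permission and the 3-month bullet differ by about 8 to 9 weeks for a woman last dosed at Week 12. For women who stop early they differ by other amounts, and after a single dose the order reverses. Section 10.4.2, as far as it can be read, conflicts with the permission outright.

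This rests on three assumptions: that the last planned dose is at Week 12, that three months means 84 to 92 days, and that no removed text in or near 10.4.2 supplies an exception. If such text exists, the conflict inside 8.6.2 remains, because all three of its timing statements are visible.

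The consequence is inconsistent site advice on a subject-protection rule, and inconsistent labelling of the same act as permitted or prohibited. The primary and secondary efficacy results at Week 16 are untouched.

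**What to change.** The sponsor should reconcile four statements: the general requirement, the Week 16 sentence and the 3-month bullet in Section 8.6.2, and the prohibition in Section 10.4.2. The result should be one rule, stated once, that gives:

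- one start time for permitted hormonal use and one end time for the nonhormonal requirement;
- whether a calendar week, a visit or an interval from the last dose governs;
- how it applies to subjects who discontinue early;
- a matching reference in Section 10.4.2.

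Which rule to adopt is for the sponsor, and this review takes no position on it. Inclusion criterion 8 already points to 8.6.2 and needs no separate change. The SAP listing of prohibited medication should follow the reconciled rule.

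The cost is a protocol clarification and a letter to sites. No new data field is required.

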9.1 Description of Study Periods

Refer to Table 2 for an outline of procedures required at each study period and/or visit.

Prior to performing any study procedures, the Investigator (or designated personnel) will ensure that the subject is given full and adequate oral and written information about the study and the subject must sign the ICF, as described in Section 15.2.1.

9.1.1 Screening Period

Screening assessments will be performed from Day -100 to Day -1. Subjects will be requested to attend the clinic after a 10-hour fasting period (except for water intake). All Screening evaluations must be completed and reviewed to confirm that potential subjects meet all eligibility criteria. Subject must have:

• at least 2 menstrual cycles with an interval of 21 to 38 days prior to treatment Day 1

[figure not shown]
A TVU may be scheduled and performed at any time during the Screening period (refer to Section 10.18.4 for further details).

9.1.1.1 Washout Period (if applicable)

If applicable, subjects will complete a Washout period (approximatly 90 days) of hormonal therapies and must have a mentrual cycle with an interval of 21 to 38 days prior to entering the Screening period. For further details or any questions to assess the eligibility for the Screening period, please call the medical monitor.

Subjects who have received any of the following will require a Washout period as described in the Table 3.

[figure not shown]
Non-hormonal IUD is not required to be removed if a patient has had no adverse reactions (eg, anemia, backache, dysmenorrhea, dyspareunia, expulsion [complete or partial], prolonged menstrual flow, menstrual spotting, pain and cramping, and vaginitis) due to the non-hormonal IUD for more than 3 months before study participation.

Protocol MT-2990-A01

Confidential

Page 48 of 103

9.1.2 Re-screening

If a subject has not met all eligibility criteria at the end of the Screening period, the subject will be registered as a screen fail. Screen fail subjects may be eligible for re-screening one time. If subject is screen failed due to laboratory measures only, a total 2 re-screenings > 2 weeks apart can be performed. For technical errors, please contact medical monitor.

[figure not shown]
Rescreened subjects must first be registered as screen failures and subsequently registered as rescreens. Once the subject is registered as rescreened, a new Screening window will begin. The rescreened subject will be assigned a new unique Subject Identifier and the previous Subject Identifier will be noted. If the re-screening period begins more than 30 days after the original signing of the ICF, all Screening procedures, including ICF, must be repeated.

9.1.3 Double-Blind Treatment Period

Subjects who successfully complete the Screening period will return to the study clinic on Day 1 and inclusion and exclusion criteria will be reviewed to confirm eligibility. Subjects will be requested to attend the clinic after a 10hour fasting period (except for water intake).

ligible subjects will then be randomized and dosing will begin on Day 1 (Visit 2).

Site staff will monitor e-Diary compliance and contact subjects to rectify, if noncompliant. Subjects and sites will be auto-notified by e-Diary vendor if the subject is noncompliant

Protocol MT-2990-A01

Confidential

Page 49 of 103

(eg, missed/erroneous data entry).

9.1.4 Extended Follow-up Period

Extension visits will be conducted via a telephone call at Week 27 (Visit 10) within \pm 14 days and at Week 38 (Visit 11) within \pm 14 days.

9.1.5 Early Termination

For all subjects, Visit 9 ([ET], Week 16) assessments should be performed, per the Schedule of Assessments (Table 2).

Any unresolved AE or SAE will be followed up according to Section 12.

In the event that a subject elects not to return to the clinical site for the ET Visit, the Investigator must make every effort to contact the subject to review all AEs. In the event that a subject drops out of the study at any time, the reason for discontinuation must be fully documented in the source documents and the eCRF. The Investigator site personnel will document the AEs and any other assessments in the source documents and will make every effort to complete all required EOS assessments.

9.1.6 Unscheduled Visits

An unscheduled visit is defined as any visit to the Investigator site outside of the protocol specified time points due to safety reasons or when a repeated measurement is required (eg, obvious measurement errors, measuring device failure, confirmation of out-of-range results), where the subject is seen by study personnel.

Additional unscheduled safety assessments such as routine blood sampling may be performed at the discretion of the Investigator, if deemed necessary. All unscheduled visits and assessments performed during the visits will be recorded in the eCRF.

9.1.7 Poststudy Access to Treatment

MT-2990 will not be available to subjects following study termination or completion of the study in accordance with study information that has been provided to the subject.

10 STUDY PROCEDURES

10.1 Informed Consent Form

The Investigator or designee will fully explain the nature of the study to subjects using the IRB-approved ICF. When the subject agrees to participate in the study, the subject must voluntarily sign an ICF prior to the initiation of any study procedures. A copy of the signed and dated ICF will be given to the subject. The signed and dated original ICF will be retained by the Investigator. Informed consent will be obtained from all subjects. A subject cannot be entered into the study until she has signed and dated the ICF. The Investigator or designee is responsible for ensuring that the subject understands the risks and benefits of participating in the study, including answering any questions the subject may have throughout the study and sharing any new information in a timely manner that may be relevant to the subject's willingness to continue her participation in the study. Refer to Section 15.2.1 for further details.

10.2 Demographics

Demographics will include date of birth, sex, weight, height, ethnicity, and race.

10.3 Medical History

Medical history will include any significant, relevant past conditions, and any current medical conditions including drug use, smoking, alcohol, or surgeries.

10.4 Prior and Concomitant Medications

At the Washout and Screening Periods, subjects will be asked what medications they have taken during the last 3 months and all medications will be recorded as prior medications in the subject's source documents.

Concomitant medication is defined as any medication, other than the study medication, which is taken during the study from the Washout and Screening Periods to the EOS Visit, including prescription, herbal and over-the-counter medications. All concomitant medications taken while the subject is participating in the study will be recorded in the eCRF.

10.4.1 Permitted Medication

Medicines, which, in the opinion of the Sponsor and Investigator, will not interfere with the study procedures or compromise safety may be used (eg, occasional use of acetaminophen for

mild analgesia). However, any other concomitant medication will be given only if deemed necessary by the Investigator or the subject's personal physician.

10.4.2 Prohibited Medication

Subjects must not participate in any other clinical study involving administration of an IMP for the duration of the current study.

Subjects must not take any prescribed or nonprescribed systemic or topical medication (including herbal remedies) unless, in the opinion of the Investigator and Sponsor, the medication will not interfere with the study procedures or compromise safety.

Subjects must not take hormonal contraceptives.

10.5 Immunogenicity and Pharmacokinetic Sampling

[figure not shown]
The timings of blood sampling to measure anti-MT-2990 antibody and PK assessments are presented in Table 2 but may be subject to change based on the ongoing review of data.

[figure not shown]
Additional blood samples may be taken from each subject; however, the maximum volume of blood withdrawn per subject will not exceed the limit detailed in Section10.18.6. Any changes to the scheduled times of immunogenicity and PK assessments will be agreed between the Sponsor and Investigator and documented in the Trial Master File (TMF).

[figure not shown]
At agreed time points, immunogenicity and PK samples will be collected. Immunogenicity sample will be divided into anti-drug antibodies (ADA) and neutralizing antibody (NAb) sample. These samples will be packed in dry ice and sent by courier from the clinical site to the Central laboratory for later transmission to the analytical laboratories.

Contingency (back-up) ADA, NAb and PK samples will be retained at the clinical site and shipped separately to the primary samples.

PK analysis will be performed only on samples from subjects receiving MT-2990. ADA assay will be performed on all samples and NAb assay will be performed on ADA positive samples. Analyses will be performed using standard methods.

10.18 Safety Assessments

Refer to Section 12 for details of AE management.

10.18.1 Physical examination

A complete physical examination will consist of a routine assessment of major body systems: abdominal, cardiovascular, general appearance, head, eyes, ears/nose/throat, lymph nodes, musculoskeletal, neck, neurological, dermatological, breast, respiratory, and other.

A routine physical examination will consist of the following body systems: abdominal, cardiovascular, general appearance, respiratory, and other.

10.18.2 Vital signs

Sitting blood pressure (systolic and diastolic) will be measured at all study visits, including Screening where vital signs are to be assessed. Sitting blood pressure will be measured using an automatic blood pressure recording device with an appropriate cuff size, after the subject has rested for at least 5 minutes in a sitting position. The same arm will be used for all measurements where possible. The Investigator will perform an overall evaluation of vital sign findings outside of the normal range for safety purposes; such results will be reported as either 'abnormal clinically significant (CS)', or 'abnormal not CS (NCS)'. Pulse rate and tympanic body temperature will also be measured. Abnormalities of clinical significance will be reported as AEs. Repeat measurements will be performed, if needed. In addition, at Visit 2, 5, 6 and 7, vital signs will also be measured at 15±5 minutes, 30±5 minutes and 60±10 minutes post study drug infusion.

